7.10 End-of-Study Procedures for Subjects that Withdraw from the Study

Subjects that withdraw from the study must have all EOS/early termination (ET) procedures performed. Subjects should be encouraged to remain at the clinical unit until Day 16 for EOS/ET procedures. The purpose of this visit is to conduct final assessments on or as near as possible to the final day of dosing.

7.11 14-Day Safety Follow-Up

All subjects will be contacted by telephone 14 days (± 4 days) following the final dose of study drug on Day 14. The subject will be queried regarding their overall health and well-being. This telephone contact may be used to verify the resolution of any AEs that were ongoing at the time of the Day 16/ET visit. Any follow-up deemed medically necessary will be conducted as an unscheduled/safety visit, detailed in [Section 7.12](#).

Abnormal lab findings will be closely monitored by the Sponsor and repeated as deemed necessary until resolution and followed up by the treating physician. All safety data will be

reviewed by the Sponsor for any potential safety signals that would alter the safety profile of the molecule.

7.12 Unscheduled Safety Visit

The investigator may schedule an unscheduled/safety visit at the clinical unit at any time, if clinically warranted. Unscheduled and/or repeat assessments, including additional laboratory tests or investigations, may be conducted. The medical monitor should be contacted, as appropriate.

[figure not shown]
8 INVESTIGATIONAL PRODUCT MATERIALS AND MANAGEMENT

8.1 Treatments Administered

ACER-801 (osanetant) (Figure 2) is a white to almost white powder. ACER-801 is freely soluble in dichloromethane, sparingly soluble in acetonitrile and 2-propanol, and practically insoluble in water.

8.2 Identity of Investigational Product

Figure 2 Chemical Structure of ACER-801

All investigational product will be manufactured according to Good Manufacturing Practices.

8.3 Investigational Product Packaging, Storage, and Labeling

The molecular formula of ACER-801 is $C_{35}H_{41}N_3O_2Cl_2$

The molecular weight of anhydrous ACER-801 is 606.63 g.

ACER-801 capsules are stored in high density polyethylene bottles with a child resist cap.

The clinical supplies as packaged should be stored between 15-25 °C (59-77 °F), limited excursions permitted up to 30 °C (86 °F).

8.4 Investigational Product Receipt, Accountability, and Disposal

Acer's representative will send investigational product to the clinical unit under appropriate storage conditions. All shipments of investigational product should be unpacked, and the contents reviewed immediately upon receipt. If it is not possible to verify the contents immediately, they must be stored under the appropriate storage conditions until verification of the contents is possible (ideally, within 1 business day from receipt). The pharmacist or designee should verify the investigational product against the shipment documentation. The pharmacist or designee should contact Acer immediately to report any concerns regarding the shipment.

All investigational product will be provided for use only in this study and is not to be used for any other purpose. The investigator or designee will maintain a full record of investigational product accountability, including records of individual subject dispensing and final return or disposition (as directed by Acer).

Unused study drug may be destroyed on site, per the clinical unit's SOPs, but only after Acer or its designee has granted approval in writing. Acer or its designee must account for all study drug in a formal reconciliation process prior to study drug destruction. All study drug destroyed on site must be documented, and documentation must be provided to Acer or its designee and retained in the investigator's study files. The clinical unit should return unused study drug only if instructed to do so by Acer or its designee. The return of study drug or study drug materials must be accounted for on a study drug returns form provided by Acer or its designee.

The clinical research associate (CRA) who serves as the study monitor will review accountability records against investigational product dispensed and that remaining in stock during on-site monitoring visits, and when the study is completed or if it is prematurely terminated. The CRA will retrieve documentation detailing and confirming the return or destruction of the investigational product. If the investigational product is to be returned to Acer's vendor for destruction, the CRA will also prepare the investigational product for shipment.

9 PHARMACOKINETICS

All blood samples for PK analysis will be processed by a central bioanalytical laboratory. Instructions for collection, processing, storing, and shipping of PK blood samples will be provided to the clinical unit by the bioanalytical laboratory.

9.1 Blood Sampling

Blood samples will be collected for measurement of plasma concentrations of ACER-801 and its metabolite at the following time points:

Day 1 and Day 14: predose (within 30 minutes prior to dosing) and at 0.5; 1.0; 1.5; 2.0; 2.5; 3.0; 4.0; 5.0; 6.0; 8.0; 12.0 (prior to evening dose), and 15.0 hrs post morning dose

Day 2 and Day 7: predose (within 30 minutes prior to dosing)

Day 15 and Day 16: 24 hrs and 48 hrs after the morning dose on Day 14

Plasma samples will be stored at approximately -80°C for PK analyses for up to 12 months after the end of the study.

The actual time of study drug ingestion and each blood sample collection must be recorded.

9.2 Analytical Method

A validated bioanalytical method will be used for sample analysis.

10 EFFICACY ASSESSMENTS

Subjects will record VMS, including NTA, in a continuous hot flash diary during the Screening Period (2 weeks prior to Day -1) to assess eligibility. During confinement subjects will record VMS using a continuous hot flash diary. A description of the methods for VMS assessments is described in Sections 10.1 and 10.2.

10.1 Continuous Hot Flash Diary

During the 2 weeks prior to randomization, subjects will be asked to complete the continuous hot flash diary (during the day and at night). Subjects also will be required to record daily bedtime and morning wake up time. This will require recording the occurrence and severity of the hot flash (on a scale from 1 to 3).

While in the clinic (Day -1 to Day 16), subjects will continue to record the occurrence and severity (scale of 1 to 3) of each hot flash in the continuous hot flash diary (during the day and at night). Subjects also will be required to record daily bedtime and morning wake up time.

10.2 Exposure-Response Analysis

Graphical representation between efficacy measurements and plasma concentrations of ACER-801 and its metabolite will be generated to determine any potential relationships.

11 ASSESSMENT OF SAFETY

Subjects will be monitored throughout confinement for adverse reactions to the study treatments and/or procedures. Safety will be assessed by monitoring Aes/serious Aes (SAEs); vital signs; concomitant medications; physical examinations; ECGs; and clinical laboratory tests.

All Aes, whether observed by the investigator, reported by the subject, noted from laboratory findings, or identified by other means, will be recorded from the time of check-in until the subject completes the EOS assessments. Recording Aes/SAEs in the electronic data capture (EDC) system is the method for reporting Aes/SAEs. All Aes/SAEs will be recorded in the EDC.

11.1 Adverse Events and Serious Adverse Events

11.1.1 Definitions of Adverse Events

11.1.1.1 Adverse Event

An AE is defined as any untoward medical occurrence associated with the use of the investigational product in humans, whether or not considered related to investigational product. An AE can be any unfavorable and unintended sign (e.g., an abnormal laboratory finding), symptom, or disease temporally associated with any use of the investigational product, without any judgment about causality and irrespective of route of administration, formulation, or dose, including an overdose.

Adverse events include but are not limited to: (1) a worsening or change in nature, severity, or frequency of condition(s) present at the start of the study; (2) subject deterioration due to primary illness; (3) intercurrent illness; and (4) drug interaction.

Subjects should be questioned in a general way, without leading the subject or asking about the occurrence of any specific symptom. The investigator should attempt to establish a diagnosis of the event based on signs, symptoms, and/or other clinical information. The diagnosis and not the individual signs/symptoms should be documented as the AE. For example, if the underlying disease process is a stroke, it would not be appropriate to record the AE by describing the symptoms “sudden numbness, dizziness, and difficulty speaking”. The AE medical term of “stroke or cerebrovascular accident” should be recorded as it more accurately describes the AE.

All Aes must be graded for severity (i.e., intensity) using Common Terminology Criteria for Adverse Events (CTCAE) version 5.0. The investigator will determine the severity of each AE and will record it on the AE eCRF, using the categories defined in [Table 3](#). It should be noted that the term “severe” used to grade intensity is not synonymous with the term “serious”. The assessment of severity is made regardless of investigational product relationship or of the seriousness of the AE. When reporting Aes, reference should be made to the CTCAE manual for guidance on appropriate grading.

Table 3 Severity of Adverse Events

Grade	Clinical Description of Severity
1 = Mild	Asymptomatic or mild symptoms, clinical or diagnostic observations only, or intervention not indicated.
2 = Moderate	Minimal, local, or noninvasive intervention indicated; or limiting age-appropriate instrumental activities of daily living ^a
3 = Severe	Medically significant but not immediately life-threatening, hospitalization or prolongation of hospitalization indicated, disabling, or limiting self-care activities of daily living ^b
4 = Life threatening	Life-threatening consequences. Urgent intervention indicated.
5 = Death	Death related to AE.

^aInstrumental activities of daily living refer to preparing meals, shopping for groceries or clothes, using the telephone, managing money, etc.

^bSelf-care activities of daily living refer to bathing, dressing and undressing, feeding self, using the toilet, taking medications, and not bedridden.

The investigator will document their opinion of the relationship of the AE to treatment with the investigational product using the criteria outlined in Table 4. An AE for which there is a “reasonable possibility” that the investigational product caused the AE is otherwise referred to as suspected adverse reaction. “Reasonable possibility” means there is evidence to suggest a causal relationship between the investigational product and the AE.

If the relationship between the AE/SAE and the investigational product is determined to be “definite”, “probable”, or “possible”, the event will be considered to be related to the investigational product for the purposes of expedited regulatory reporting.

Table 4 Relationship of Adverse Events to Investigational Product

Relationship	Description
Definite	A reaction that follows a reasonable temporal sequence from administration of the investigational product or in which the investigational product level has been established in body fluids or tissue; that follows a known or expected response pattern to the suspected investigational product; and that is confirmed by improvement on stopping or reducing the dosage of the investigational product, and reappearance of the reaction on repeated exposure.
Probable	A reaction that follows a reasonable temporal sequence from administration of the investigational product; that follows a known or expected response pattern to the suspected investigational product; that is confirmed by stopping or reducing the dosage of the investigational product; and that could not be reasonably explained by the known characteristics of the subject's clinical state.
Possible	A reaction that follows a reasonable temporal sequence from administration of the investigational product; that follows a known or expected response pattern to the suspected investigational product; but that could readily be produced by a number of other factors.
Unlikely	An event that does not follow a reasonable temporal sequence from administration of the investigational product; that does not follow a known or suspected response pattern to the suspected investigational product; and that could reasonably be explained by known characteristics of the subject's clinical state.
Not Related	Any event that does not meet the above criteria.

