The investigator will assess whether the event is causally related to the investigational product. Acer will also assess whether the event is causally related to the investigational product, in addition to assessing the overall safety profile of the investigational product. Acer will notify the appropriate regulatory agencies of expedited safety reports that occur during the study within the time frames required by each regulatory agency.

An SAE assessed with a possible, probable, or definite causal relationship to the investigational product and unexpected according to the IB, is known as a suspected unexpected serious adverse reaction (SUSAR) and will be expeditiously reported to regulatory authorities and investigators, as appropriate.

Following the initial report, any additional information obtained by the investigator about the SAE must be reported promptly to Acer in the same manner as described above for the initial SAE report. Any supporting source documentation should be emailed to [contact] as soon as possible.

The investigator is responsible for submitting information on expedited safety reports received from Acer to their local IRB, as directed by the local-country requirements.

Documentation of the submissions to IRBs must be retained in the appropriate study files. As instructed by Acer, expedited safety reports should be retained in the appropriate investigative site study files, or with the IB.

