11.2.5 Follow-Up of Adverse Events and Serious Adverse Events

All Aes must be followed during the study until the AE resolves, is no longer of clinical concern, has stabilized or is otherwise explained, or the subject is lost to follow-up. Ongoing Aes will be monitored (telephone call) until resolution or for 30 days, whichever is first.

Abnormal lab findings will be closely monitored by the Sponsor and repeated as deemed necessary until resolution and followed up by the treating physician. All safety data will be reviewed by the Sponsor for any potential safety signals that would alter the safety profile of the molecule.

Any Aes ongoing at the final visit that are deemed to be possibly, probably, or definitely related to the investigational product or of other clinical significance must be followed for as long as necessary to adequately evaluate the safety of the subject or until the event stabilizes, resolves, or is no longer of clinical concern. If resolved, a resolution date for the AE should be documented on the eCRF. The investigator must ensure that follow-up includes any supplemental investigations indicated to elucidate the nature and/or causality of the AE. This may include additional laboratory tests or investigations or consultation with other healthcare professionals, as considered clinically appropriate, by the investigator.

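### Table 4 grades a new reaction with plausible timing as Not Related, because all three related grades require a known or expected response pattern

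*Combined protocol and SAP*

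**What the plan says.** Section 11.1.1.1 has the investigator grade causality by the criteria in Table 4. Its five rows are:

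- **Definite:** plausible timing (or a measured drug level), a reaction "that follows a known or expected response pattern to the suspected investigational product; and that is confirmed by improvement on stopping or reducing the dosage", and recurrence on re-exposure.
- **Probable:** plausible timing, a reaction "that follows a known or expected response pattern to the suspected investigational product; that is confirmed by stopping or reducing the dosage", and no reasonable explanation in the subject's clinical state.
- **Possible:** a reaction which "follows a known or expected response pattern to the suspected investigational product; but that could readily be produced by a number of other factors", again with plausible timing.
- **Unlikely:** "An event that does not follow a reasonable temporal sequence from administration of the investigational product", which also fits no known or suspected pattern and can be explained by the clinical state.
- **Not Related:** "Any event that does not meet the above criteria".

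Just above the table, the same section defines a suspected adverse reaction by a reasonable possibility of causation, which "means there is evidence to suggest a causal relationship between the investigational product and the AE". It counts only the top three grades as related for expedited reporting. Section 11.2.2 says that an SAE graded possible, probable or definite and "unexpected according to the IB, is known as a suspected unexpected serious adverse reaction (SUSAR"). Section 11.2.5 continues follow-up after the final visit for events "deemed to be possibly, probably, or definitely related to the investigational product or of other clinical significance must be followed". Section 12.6.2 tabulates adverse events by relationship, among other breakdowns.

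**The concern.** Causality grading should be able to recognise a reaction nobody has seen before. Here the investigator must first find that the event fits a known or expected pattern before any related grade is open. A new reaction cannot meet that condition, and if its timing is plausible it cannot be Unlikely either.

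The protocol offers little pattern to match against. Section 2.2 reports that the commonest adverse events on osanetant occurred at rates comparable with placebo. The earlier patient groups it lists are schizophrenia, depression, panic disorder, Parkinson's disease and asthma. The Investigator's Brochure (IB) may say more, but it is not among the documents.

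At stake are the investigator's causality label and what depends on it: the table by relationship, part of the follow-up rule, and the relatedness half of the SUSAR definition.

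**Working it through.** The plan gives no figure to reproduce. The check is whether the rows of Table 4, read as written, give the grade claimed.

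**Conditions (yes/no), all from Table 4.** T: reasonable timing. L: drug level established. P: known or expected pattern. S: known or suspected pattern (the wording in Unlikely). D: improvement on stopping or reducing (dechallenge). R: recurrence on re-exposure (rechallenge). C: explained by the clinical state. F: readily produced by other factors.

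**Rules, applied from the top down.**

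- Definite = (T or L) and P and D and R
- Probable = T and P and D and not C
- Possible = T and P and F
- Unlikely = not T and not S and C
- Not Related = everything else

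**Number of cases.** P implies S, which leaves 3 (P, S) pairs. R implies D, which leaves 3 (D, R) pairs. T, L, C and F are free, giving 2^4 = 16. Total: 3 × 3 × 16 = 144.

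**Results.**

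| Subset | Cases | Definite / Probable / Possible | Unlikely | Not Related |
|---|---|---|---|---|
| No known or expected pattern | 2 × 3 × 16 = 96 | 0 | 12 | 84 |
| The same, plausible timing | 48 | 0 | 0 | 48 |
| The same, with dechallenge and rechallenge positive and no other explanation (C and F both no) | 4 | 0 | 0 | 4 |
| Known pattern, plausible timing | 24 | 8 / 4 / 6 | 0 | 6 |
| The same, no dechallenge, no other factors | 4 | 0 | 0 | 4 |

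The third row is the main defect: the strongest causal evidence the table recognises still gives Not Related. The last row is a second gap. Without dechallenge the event is neither Definite nor Probable, and because nothing else readily explains it, it fails Possible as well. An event is thus graded lower for lacking a competing cause.

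**Set against the text.** The reasonable-possibility sentence asks for evidence of causation and has no pattern condition, so one event can meet it and still be Not Related in the table below it. The SUSAR definition needs a top-three grade, which Table 4 gives only to known or expected patterns, and also needs the event to be unexpected per the IB. The overlap is an event that fits a known pattern but is not listed in the IB.

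**Would dropping the pattern condition be enough?** With P removed from the three related grades, the 48 cases become 16 Definite, 8 Probable, 12 Possible and 12 Not Related. The remaining 12 all have F = no. Eight have no dechallenge (2 × 2 × 2 over L, S and C). Four have dechallenge without rechallenge and C = yes (2 × 2 over L and S). Possible must therefore also stop requiring another candidate cause.

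These are counts of logical combinations. They show where the rules lead and say nothing about how often such events occur.

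**The case against.** The strongest reply is that Table 4 governs only the investigator's opinion, and other safeguards surround it.

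- **Capture.** Section 11.2.2 sends every SAE to the sponsor within 24 hours whatever its relationship, and Section 11.2.4 covers all SAEs within 30 days of stopping. This stands in full.
- **Sponsor's assessment.** Under Section 11.2.2 the sponsor also judges causality and is not told to use Table 4. The SUSAR sentence does not say whose judgement counts. A reader might infer that a serious new reaction would certainly escape expedited reporting. The documents do not show that, because this route is open. It is only ambiguous: no sponsor criteria are given, and the three grade terms are defined nowhere but Table 4.
- **SUSARs remain possible.** Fitting a response pattern and being listed in the IB are different tests. Section 2.2 mentions liver findings in toxicology studies that were not seen in controlled trials. An event fitting such a pattern might still be unlisted.
- **Endpoints.** A reader might infer bias in the primary safety objective. The safety endpoints in Section 12.3.2 (examination and laboratory changes, adverse events of at least 5%, all SAEs and discontinuations) do not use relatedness. Incidence by arm, against placebo, is unaffected.
- **Other cover.** Follow-up in Section 11.2.5 extends to events of other clinical significance, and the review triggers in Section 5.6 do not wait for a relatedness grade.
- **Prior experience.** Osanetant has 23 completed studies, with about 400 Phase 1 subjects and 821 Phase 2 patients, so some pattern knowledge exists.
- **The second gap is narrow.** An event still present at the planned end of dosing on Day 14 that then improves could be read as dechallenge. The gap mainly concerns one-off events that are over before dosing stops, or effects that persist.

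These points limit the consequences. None of them changes the grade that Table 4 assigns, and expecting investigators to look past the table would concede that it needs rewording.

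**Conclusion.** The point holds as a wording error in a stated rule. Read literally, Table 4 assigns Not Related to every new reaction with plausible timing (48 of 48 combinations), and to known-pattern events with plausible timing but neither dechallenge nor another likely cause (4 of 4). It contradicts the reasonable-possibility standard in its own section and leaves the SUSAR definition with a narrow overlap on the investigator's grade.

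The effect reaches causality labels, the by-relationship table, relatedness-based follow-up and possibly expedited classification. Certain loss of expedited reports and bias in the listed safety endpoints are not supported.

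The conclusion assumes that each row's clauses are cumulative, as their punctuation and conjunctions indicate, and that investigators apply the table as written. How narrow the SUSAR overlap is depends on the IB.

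**What to change.** Reword Table 4 and the matching form guidance:

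1. Make response pattern a supporting factor for Definite, Probable and Possible, not a required condition.
2. Let Possible include any event with reasonable timing and evidence suggesting causation, whether or not other factors could explain it. Do not widen this to any event where a drug role cannot be excluded, which would go beyond the protocol's own evidence test.
3. Define Not Related positively and without overlap with Unlikely. One workable split for events below Possible: Not Related where another cause is established or onset preceded exposure, and Unlikely for the rest. The Unlikely row would then change too, so that the five rows cover each event once.
4. State that Possible or higher is the reasonable-possibility test of Section 11.1.1.1, and that investigator and sponsor both use it for the SUSAR definition in Section 11.2.2.

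The cost is an edit to one table, a linking sentence and the form guidance, with no new procedures. The downside is that a few more events will be graded related.
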